Since its introduction, low-molecular-weight heparins (LMWHs) are still common used in practice as thromboprophylactic agent. But, they require subcutaneous administration which making it challenging for use in settings other than the inpatient one. Despite the lower incidence of low-molecular-weight heparins (LMWHs) induced heparin-induced thrombocytopenia (HIT) compared with unfractionated heparins (UFH) in the postoperative setting, the risk of LMWH induced HIT in patients treated for VTE still concerns many clinicians. In addition to its subcutaneous administration, fondaparinux is contraindicated in severe renal impairment patients (with creatinine clearance (CrCl) <30 milliliter/minute) and those who have low body weight (<50 kg; VTE prophylaxis only). While available orally, Vitamin K antagonists (VKAs) like Warfarin have unpredictable pharmacologic effects requiring a wakeful monitoring. Warfarin is also a remarkable source of food and drug interactions. As a result, it is mandatory to search for novel drugs or at least to search for new indications of really existing drugs. [2]

In July 2011, the Food and Drug Administration (FDA) approved an orally administered selective factor Xa inhibitor called Rivaroxaban for the prevention of deep vein thrombosis (DVT) after total hip replacement (THR) or total knee

replacement (TKR) surgeries. According to the Regulation of Coagulation in Orthopedic Surgery to Prevent Deep Vein Thrombosis and Pulmonary Embolism (RECORD) trials, rivaroxaban demonstrated superiority to enoxaparin in reducing venous thromboembolism without significant increase of bleeding risk. Rivaroxaban is recommended to be used at a fixed dose of 10 mg daily, with or without food, for 35 days following THR or 12 days following TKR. [3]

Although the US Food and Drug Administration (FDA) advisory committee has recommended approval of rivaroxaban, many questions have been raised on the Regulation of Coagulation in Orthopedic Surgery to Prevent Deep Vein Thrombosis and Pulmonary Embolism (RECORD) trials of rivaroxaban. Some may argue that dosing was inconsistent with the recommendations. Others went far to say that the duration of treatment was inconsistent and did vary with enoxaparin. In other words, it was somewhat short.

Results from the ORTHO-TEP registry on joint replacement arthroplasty (hip and knee) from Dresden, Germany and Xarelto® in the Prophylaxis of Postsurgical Venous Thromboembolism after Elective Major Orthopaedic Surgery of the Hip or Knee (XAMOS) study are in accordance with the conclusion of Regulation of Coagulation in Major Orthopedic surgery reducing the Risk of DVT and PE (RECORD) trials. A subset of countries that participated in XAMOS also included patients undergoing fracture-related orthopedic surgery. [1,3,4]

Surgery as a therapy for cancer may double the risk of venous thromboembolism. However, results from studies including SAVE-ONCO, PROTECHT, and FRAGEM have been used as a backbone of recommendation for VTE prophylaxis in cancer patient, no controlled one has compared the new anticoagulant like Rivaroxaban with the standard of care therapy drugs [6]. All these new drugs including rivaroxaban have not been intensively studied in patients undergoing day-surgery. High risk VTE ambulatory surgical patients such as patients with a previous episode of VTE or with additive risk factors may benefit from rivaroxaban. [7].

It is a hot topic of debate to accept standard method of VTE prevention in plastic surgery. In a retrospective experience of 2 surgical centers that use rivaroxaban for routine VTE prophylaxis for patients undergoing abdominoplasty, Oral rivaroxaban administration for chemoprophylaxis in abdominoplasty patients is safe, with low

rates of symptomatic VTE and hematoma formation. The authors recommended routine use of the medication for patients at increased risk for VTE events. Regarding other trials that compare rivaroxaban by standard of care drugs, we can't find direct comparison between the two regimens. [8]

Similarly, no controlled trials have evaluated the role of rivaroxaban as a new oral anticoagulant in Venous thromboembolism (VTE) prophylaxis for other nonorthopedic surgical patients. According to American College of Chest Physicians (ACCP), 2012 recommendation for thromboprophylaxis for general, abdominal-pelvic surgery, thoracic, cardiac surgery and Gynecological surgery, it is recommended to weigh the risk of thrombosis against the bleeding risk before adding LMWH or unfractionated heparin.

Moreover, very few randomized clinical trials (RCTs) are powered to study side effects when comparing substances, and even large RCTs may be too small to reveal rare side effects. It seems difficult to compare safety data from trial to trial because there is no standardized definition of bleeding. One prospective study collecting data from the electronic health record at two institutions concluded that using of enoxaparin for VTE prophylaxis following THA and TKA was associated with a lower rate of the primary outcome (any postoperative bleeding) compared with the use of rivaroxaban in a similar cohort of patients. However, it was a retrospective investigation with many limitations can be argued with regard to selection and change in practice guideline during the study period.

Finally, there is lack of literature data that define rivaroxaban as orthopedic postoperative thromboprophylactic agent rather than well-known indications (hip and knee replacements). It also is not plausible to accurately compare safety data with other injectable anticoagulants.

Aim of the work

The main objective is to reduce the incidence of venous thromboembolism (VTE) in orthopedic postoperative patients based on the potential benefit of using rivaroxaban as a monotherapy.

It is around efficacy and safety evaluation of using rivaroxaban as a monotherapy prophylactic agent in patients undergoing orthopedic surgeries taking into the account the reliable selection of patients most benefit.

Answering questions about additional cost benefit from the perspective of the cost-effective analysis on extrapolating the results emerged to our university teaching hospital setting are going to be evaluating as well.

Methodology

Study design and randomization

It is proposed to randomly assign at least 100 patients sequentially based on admission; in a single blind, interventional trial, to two separate groups. Patients are going to be selected from our university teaching hospital. patients were randomly assigned to a study group with the use of permuted blocks and stratification using well trusted randomization websites or software programs (SAS). Permuted block randomization list will be transferred from alphabetic symbol by the competent orthopedic supervisor and coded based on the randomization order by manual coding preset by orthopedic supervisor [5]. Double dummy technique may be feasible here as long as we tackled difficulty of providing syringes containing saline. However, the risk of injecting a saline solution subcutaneously (i.e. bleeding complications may develop in persons taking an anticoagulant agent plus unnecessary injections) may outweigh the benefit. Since the investigator do not know which therapy is administrated, the potential for the results to be biased is minimized [6].

The first group is to be on rivaroxaban with dosage according to the orthopedic approved regimen (10 mg once daily 6-10 hours after the surgery; recommended total duration of therapy: 12 to 14 days; ACCP recommendation: Minimum of 10 to 14 days; extended duration of up to 35 days suggested (Guyatt 2012).[3]

The other group will be administered the standard of care (SOC) enoxaparin. Dosage and duration of therapy are illustrated in Table 1 [2].

Drug	Dosage and Duration
Enoxaparin	Once-daily dosing: 40 mg once daily, with initial dose within 9 to 15 hours before surgery, and daily for at least 10 days (or up to 35 days postoperatively) or until risk of DVT has diminished or the patient is adequately anticoagulated on warfarin. The American College of Chest Physicians recommends initiation ≥ 12 hours preoperatively or ≥ 12 hours postoperatively; extended duration of up to 35 days suggested (Guyatt, 2012).

Table 1: *Dosing of SOC drugs used in thromboprophylaxis after orthopedic surgery.*

It is expected here that all medication will be taken for a duration of 10 days after surgery. The type, duration and dose of the thromboprophylactic agents will be discussed with and determined by the competent physician before saying a particular patient can be enrolled.

Study population

The Patients >18 years who are going to be scheduled to undergo orthopedic surgery in whom decision of thromboprophylaxis taken will be enrolled for inclusion.

Exclusion criteria are based on the approved contraindication listed, for all drugs used, in the drug’s labels and supplemented by data from well trusted compendia like Lexi comp® or Micromedex®. The exclusion criteria are as follows, but not limited to:

- I. Severe hypersensitivity to drugs or any component of the formulation.
- II. Planned intermittent pneumatic compression
- III. A requirement for anticoagulant therapy that could not be stopped
- IV. Severe hypersensitivity reaction (eg, anaphylaxis) to rivaroxaban or enoxaparin.
- V. Received another anticoagulant for more than 24 hours
- VI. Active bleeding or a high risk of bleeding
- VII. Thrombocytopenia associated with a positive test for antiplatelet antibody.
- VIII. Warfarin associated INR more than 1.5 on the day of the surgery
- IX. Conditions preventing bilateral venography
- X. ICU stay after surgery
- XI. Pregnant or breast-feeding

- XII. Creatinine clearance less than 30 ml per minute or acute renal failure before the surgery or at any point during the study period.
- XIII. Moderate or Severe (Child Pugh B or C) hepatic Impairment or in patients with any hepatic disease associated with coagulopathy.
- XIV. Concomitant use of drugs that are both p-glycoprotein inhibitors and moderate to strong cyp3a4 (ketoconazole, itraconazole, lopinavir/ritonavir, ritonavir, indinavir/ritonavir & conivaptan)
- XV. CrCl 15 to 80 mL/min PLUS both P-glycoprotein inhibitors and moderate CYP3A4 inhibitors (eg, abiraterone acetate, diltiazem, dronedarone, erythromycin, verapamil)

The study draft will be submitted to our ethics committee attached to the hospital administration board before enrollment of patients.

Prescribed co-medication of interest.

Because of the well documented effect of drugs affecting CYP3A4 co-prescribed with rivaroxaban, strong inhibitor and inducers listed on <http://medicine.iupui.edu/clinpharm/ddis/clinical-table/> under the guidance of US Food and Drugs Administration(FDA) are contraindicate with rivaroxaban. Patient on these interacting drugs will be excluded.

Outcome measure and follow up.

The primary efficacy outcomes are the composite of any deep-vein thrombosis, nonfatal pulmonary embolism, or death up to 30 days. The main secondary efficacy outcome is major venous thromboembolism, which is defined as the composite of proximal deep-vein thrombosis, nonfatal pulmonary embolism, or death from venous thromboembolism.

The main safety outcome is the incidence of major bleeding beginning after the first dose of the study drug and up to 2 days after the last dose of the study drug (on-treatment period). Major bleeding is defined as bleeding that is fatal, occurs in a critical organ (e.g., retroperitoneal, intracranial, intraocular, and intraspinal bleeding), or requires reoperation or extra surgical-site bleeding that was clinically overt and is associated with a fall in the hemoglobin level of at least 2 g per deciliter or that requires transfusion of 2 or more units of whole blood or packed cells. Other safety outcomes include any on-treatment bleeding, any on-treatment non- major

bleeding, hemorrhagic wound complications (a composite of excessive wound hematoma and reported surgical-site bleeding), any bleeding that starts after the first oral dose of rivaroxaban and ended up to 2 days after the last dose is administered, adverse events, and death.

Validated clinical prediction rule is recommended to estimate pretest probability of venous thromboembolism. Duplex ultrasonography is the preferred test to diagnose DVT [7]. Many prediction scales are available like *Wells Clinical Models for Evaluating the Pretest Probability of VTE*.

Symptoms and signs of DVT may include unilateral leg swelling, pain in the affected leg, calf tenderness in affected leg, increased leg warmth, erythema of affected leg, or a “palpable cord” may be felt in the affected leg.

Regarding PE, diagnosis is suspected in patients with dyspnea, tachypnea, pleuritic chest pain, cough, and/or fever. Diagnosis begins with initial risk stratification based on presence of shock or persistent hypotension to identify patients at high risk of early mortality.

For patients with suspected high-risk PE with shock or hypotension, emergency computed tomography(CT) angiography beside transthoracic echocardiography is recommended depending availability and clinical circumstances. While for patients not suspected of having high-risk PE, clinical assessment of likelihood of PE using validated prediction rules and clinical judgement to distinguish between low and high-risk PE may use [8]. However, PE can be diagnosed based on computed tomography pulmonary angiography (CTPA). CT pulmonary angiography is preferred method when available.

It is recommended to have baseline Scr and platelets count. Based on Heparin induced thrombocytopenia, it is advisable to monitor platelets count beginning of the fourth day and every three days until discontinue of Heparins.

Data analysis

The patients in the two groups will be matched in advance for the difference in Patients’ characteristics, VTE risk factors, history of VTE, types of surgery, types of anesthesia and duration of surgery. This ensures fair randomization between groups. Statistical analysis will be performed at an overall significance level of 0.05, adjusted for the primary and secondary end points using non- independent t-test

(SPSS software). Comparisons of the primary end points between treatment groups were performed by means of a log-rank test. To estimate the size of the effect, we will use a Cox regression model. On the other hand, the cost-effective analysis (CEA) will be based mainly on estimating the average cost-effective ratio(ACER) and the incremental cost for each additional cure.

References

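### Randomisation is stratified, but the log-rank test and Cox model are specified without the strata: a small, nearly free improvement

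*Combined protocol and SAP*

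**What the plan says.** Study design and randomization (under Methodology) states that "patients were randomly assigned to a study group with the use of permuted blocks and stratification". It gives no stratification factor, no levels and no block size. The planned size is a minimum: "It is proposed to randomly assign at least 100 patients sequentially based on admission".

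The primary efficacy outcome, under Outcome measure and follow up, is the "composite of any deep-vein thrombosis, nonfatal pulmonary embolism, or death up to 30 days".

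Data analysis names the inferential methods in one sentence each: "Comparisons of the primary end points between treatment groups were performed by means of a log-rank test", and "To estimate the size of the effect, we will use a Cox regression model". Neither sentence mentions a stratum or a covariate.

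Two other phrases in that section might seem to supply the link, but neither does:

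- "The patients in the two groups will be matched in advance for the difference in Patients’ characteristics, VTE risk factors" opens a list that also covers VTE history, surgery type, anaesthesia type and operating time. The list is not described as the stratification factors and is not carried into either model.
- "adjusted for the primary and secondary end points using non- independent t-test" concerns end points and a t-test, not strata.

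**The concern.** Stratified permuted blocks hold the arms nearly equal within each stratum. If the strata predict the outcome, this removes chance imbalance from the treatment comparison. The variance formula of an unstratified log-rank test does not know this and still allows for that imbalance. The test statistic is then too small on average, so the true type I error falls below the nominal level and some power is lost.

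In a trial planned around 100 patients, with a composite outcome that may give few events, power is scarce. An analysis that follows the randomisation recovers whatever the strata offer. Leaving the point unstated also leaves the choice between a stratified and an unstratified analysis open until data are seen.

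**Working it through.** **The plan's own figure.** The only figure is the minimum of 100 patients. It cannot be reproduced, because no event rate, effect size, power or dropout is given. The documents contain nothing that fixes the size of this issue, so it was explored over assumed ranges.

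**Inputs from the documents.** N = 100, two groups, permuted blocks within strata, log-rank test, and alpha 0.05 ("Statistical analysis will be performed at an overall significance level of 0.05").

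**Assumed inputs.** 1:1 allocation; two-sided test; block size 4; 2, 4 or 12 strata of equal expected size; mean control event risk 10%, 20% or 40%; hazard ratio between extreme strata (the spread) 1, 3 or 9; treatment hazard ratio 1 (type I error) or 0.4 (power). There were 3000 simulated trials per scenario, and both tests were applied to the same trials.

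**Formulas.** At each event, let p be the proportion of those at risk who are in the treated arm, and let a = 1 if the event is in that arm and 0 otherwise. Then U = Σ(a − p), V = Σ p(1 − p), and the test rejects when U²/V > 3.84. The stratified version computes p within each stratum and sums U and V over strata.

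**Type I error** (range over numbers of strata and event risks):

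| Hazard spread | Unstratified | Stratified |
|---|---|---|
| 1 | 0.045 to 0.052 | 0.046 to 0.053 |
| 3 | 0.038 to 0.052 | 0.042 to 0.055 |
| 9 | 0.015 to 0.047 | 0.044 to 0.057 |

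The simulation standard error at 0.05 is √(0.05 × 0.95 / 3000) = 0.004. The unstratified test is therefore at or below 0.05 within that error. The lowest value, 0.015, occurs with two strata, a ninefold spread and 40% risk.

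**Power at hazard ratio 0.4**, unstratified → stratified:

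| Spread | Strata | 10% risk | 20% risk | 40% risk |
|---|---|---|---|---|
| 1 | 2 | 0.196 → 0.192 | 0.367 → 0.366 | 0.671 → 0.673 |
| 1 | 4 | 0.199 → 0.203 | 0.377 → 0.374 | 0.663 → 0.661 |
| 1 | 12 | 0.203 → 0.200 | 0.379 → 0.368 | 0.673 → 0.649 |
| 3 | 2 | 0.193 → 0.199 | 0.344 → 0.359 | 0.651 → 0.687 |
| 3 | 4 | 0.192 → 0.198 | 0.366 → 0.377 | 0.661 → 0.681 |
| 3 | 12 | 0.199 → 0.199 | 0.377 → 0.370 | 0.660 → 0.652 |
| 9 | 2 | 0.187 → 0.205 | 0.335 → 0.379 | 0.575 → 0.693 |
| 9 | 4 | 0.196 → 0.210 | 0.343 → 0.377 | 0.601 → 0.671 |
| 9 | 12 | 0.191 → 0.197 | 0.370 → 0.384 | 0.628 → 0.654 |

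The three risk columns correspond to about 7, 14 and 29 to 30 events per trial.

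- Spread up to 3: the change runs from 0.649 − 0.673 = −0.024 to 0.687 − 0.651 = +0.036.
- 10% risk: the largest gain is 0.205 − 0.187 = 0.018.
- Largest gain overall: 0.693 − 0.575 = 0.118.
- Twelve strata: from −0.024 to 0.654 − 0.628 = +0.026.

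**Cox model.** The mean ratio of stratified to unstratified V was 0.95 to 1.00 in the power scenarios. The standard error of a log hazard ratio is roughly 1/√V, so stratifying would leave it unchanged or raise it by up to 1/√0.95 − 1 = 2.6%. Where power rises, it is because the within-stratum hazard ratio lies further from 1 than the pooled one, not because the standard error falls.

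**The case against.** The strongest reply is that the plan is silent rather than wrong. It gives no model terms at all, so a reader who infers a decision to ignore the strata goes beyond the text. That stands: the supportable statement is that the strata are not specified in the analysis. Silence still needs repair, because a log-rank test with no strata named will be run unstratified by default.

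Second, the factors are unnamed, so nobody can say that they are prognostic. Broad entry to orthopaedic surgery shows that risk varies between patients. It shows variation between strata only if the strata track that risk. This stands too, and it is why no single figure for the loss can be given.

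Third, a reader might infer that every standard error is inflated, by an amount that can be worked out from stratum risks. For two equal strata with risks of 2% and 30%, the pooled variance is 0.16 × 0.84 = 0.1344 and the mean within-stratum variance is (0.0196 + 0.2100)/2 = 0.1148, a ratio of 1.17. For 1% and 5% it is 0.0291/0.0287 = 1.01. The arithmetic is right, but it describes a risk difference, which the plan does not propose. It does not carry over to the planned Cox hazard ratio, and on the standard-error scale even the larger case is only √1.171 = 1.082.

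Fourth, stratifying is not always free of statistical cost: twelve non-prognostic strata lost about 2 points of power at 40% risk. That stands and calls for a pooling rule.

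**Conclusion.** The point holds as a minor, nearly free improvement. Allocation is stratified, and neither the log-rank test nor the Cox model is specified with the strata, so the analysis as written does not reflect the design.

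If the strata are prognostic, the unstratified log-rank test is conservative. A reader might infer a raised false-positive rate or an invalid trial. Neither follows, because the error rate stays at or below 0.05. At about 100 patients the power gained by stratifying is likely to be small: -2 to +4 points for hazard spreads up to threefold, and under 2 points at 10% event risk. A gain of about 12 points needed two strata, a ninefold spread and 40% risk together. With many sparse strata the gain can vanish or slightly reverse.

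For the Cox model, the main consequence of stratifying is to target a within-stratum hazard ratio. The documents do not support a claim that the planned interval is too wide.

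These sizes rest on assumed event risks, prognostic strength, number of strata, block size, 1:1 allocation and a two-sided test. None of these is given in the plan.

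**What to change.** In Data analysis:

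1. Identify the stratification factor or factors, and their levels, actually used in the randomisation list.
2. Make the primary comparison a log-rank test stratified by them.
3. Stratify the Cox model by the same factors or adjust for them, and say which. Either reflects the design. State that the hazard ratio is then interpreted within strata, or conditional on the factors.
4. Prespecify how sparse strata are pooled, with the order of pooling fixed before outcomes are seen by arm.
5. Report the unstratified log-rank test and Cox model as a sensitivity analysis.

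The pooling rule matters most if the characteristics listed for matching turn out to be the strata. Six such headings at an assumed two levels each would give 2⁶ = 64 cells, or 100/64 ≈ 1.6 patients per cell.

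The cost is a few sentences, with no new visits or patients and no change to the randomisation. The plan does not say that the list records each patient's stratum. This should be confirmed, and the stratum carried into the analysis data set. A different effect measure, such as a Mantel-Haenszel risk difference, is optional and not needed to resolve this point.

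### The plan describes no allocation concealment, and one sentence, read literally, has a physician settle the agent before the patient is cleared for enrolment

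*Combined protocol and SAP*

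**What the plan says.** All the relevant text is in the combined protocol and SAP, Methodology, under Study design and randomization.

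- **Size and order of entry.** "It is proposed to randomly assign at least 100 patients sequentially based on admission". The trial is described as single blind with two groups.
- **Method.** Permuted blocks with stratification, produced "using well trusted randomization websites or software programs (SAS". Block size, strata and allocation ratio are not stated.
- **Handling of the list.** "Permuted block randomization list will be transferred from alphabetic symbol by the competent orthopedic supervisor", and it is then "coded based on the randomization order by manual coding preset by orthopedic supervisor".
- **Choice of agent.** After the enoxaparin dosing table: "The type, duration and dose of the thromboprophylactic agents will be discussed with and determined by the competent physician", and this happens before a patient is declared enrollable.
- **Blinding.** The section says that the investigator is unaware of the treatment given, and takes this to limit bias. A double-dummy design is discussed, but its risks are said possibly to outweigh its benefit, and it is not clearly adopted.

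**The concern.** Randomisation protects a comparison only if nobody who decides on a patient's entry can know or influence which arm comes next. Two features of the text leave that protection in doubt. A person in the treating specialty converts the list into treatments and sets the code, and no barrier between that knowledge and recruitment is described. In addition, the agent appears to be settled by a physician before the enrolment decision.

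If the next treatment is known or chosen in advance, a patient can be enrolled, deferred or left out according to how well the patient seems to suit it. The arms may then differ in prognosis for reasons unrelated to treatment. Adjustment can deal with recorded covariates, but not with an unrecorded clinical judgement about who should receive which drug. Data analysis names no covariate adjustment in any case.

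**Working it through.** The plan gives no figure on this point to reproduce. The check is mainly a comparison of passages.

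**1. Who can know the sequence?** The supervisor turns the list's letters into something usable and presets the code by hand. Whoever maps symbols to treatments can know the sequence. So at least one clinician in the treating specialty can know it.

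**2. What separates that knowledge from recruitment?** Nothing is described. There is no central or web release at enrolment, no pharmacy-held list, no sealed opaque envelopes and no independent custodian. The websites and SAS are mentioned as means of randomising, not as the holder or releaser of assignments. The plan does not say who keeps the code, or whether the supervisor or the physician recruits.

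**3. How does the physician sentence sit beside random assignment?**
- The opening of the section says that patients are assigned at random to one of two groups, rivaroxaban or enoxaparin.
- The later sentence says that a physician determines the type of agent before the patient can be enrolled.
- The two arms are two types of agent, so determining the type determines the arm. Both statements cannot hold literally for the same patient. This conflict does not depend on who holds the list.

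**4. Does any other text repair this?**
- *Entry in order of admission* fixes the order in which patients come up. It does not settle whether a given patient is declared enrollable. Discretion remains there, because Study population says that its exclusions are not exhaustive and does not define high bleeding risk.
- *The investigator's unawareness of treatment* concerns blinding once treatment is given. It does not describe concealment before entry, and it does not mention the supervisor or the physician.

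**5. Scale.** The plan states at least 100 patients and no allocation ratio. Assume exactly 100 and an equal split:
- Patients per arm: 100 / 2 = 50.
- One event in one arm: 1 / 50 = 0.02, or 2 percentage points of that arm's rate.
- One event moved from one arm to the other, arm sizes unchanged: 1/50 + 1/50 = 0.04, or 4 percentage points of the difference.

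This shows how coarse the comparison is. It does not estimate the bias, because the documents give no event rates and no indication of how many patients might be steered.

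**The case against.** The strongest reply is that the text is loosely worded rather than wrong.

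- *Coding by someone other than the enrolling investigator can be a way to conceal allocation.* This is true, and it stands. A reader might infer that the supervisor keeps the code, enrols patients and foresees every assignment, so that allocation is definitely unconcealed. The documents do not support that: they state neither custody nor any recruiting role. They support only the statement that no concealment is described and that at least one clinician can know the sequence.
- *The physician may merely confirm that a patient suits either regimen.* The sentence speaks of agents in the plural, and Study population already requires that thromboprophylaxis has been decided on and that contraindications to all the drugs are respected. This milder reading is possible, but the plan does not state it, and the word for type of agent points the other way. The sentence needs rewriting on either reading.
- *The plan gives no order between coding and the physician's decision.* This is correct. It cannot be said that the physician acts with the decoded list in hand, and the point does not need that.
- *Patients at high bleeding risk are already excluded.* This narrows the room for steering on bleeding risk. It does not remove it, since the criterion is undefined and the list is open-ended. Steering on thrombosis risk is unaffected.

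**Conclusion.** The point holds as a gap together with a contradiction in the text. The plan describes no allocation concealment. Its physician sentence, taken at its word, lets treatment be known or chosen before enrolment, which is incompatible with random assignment. The second part is the stronger, because it stands whoever holds the list. The matter goes beyond missing detail: staff who followed the sentence as written would undo the randomisation.

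The size of any bias cannot be derived from the documents. The figures of 2 and 4 percentage points rest on an assumed 50 patients per arm and serve only as scale. It would go too far to conclude that allocation was subverted or that the trial is not randomised, because the text shows opportunity, not occurrence. The sponsor should make the change; it is specific and cheap.

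**What to change.** 1. **Reconcile the physician sentence with randomisation.** Before enrolment, the physician confirms that the patient is eligible for both regimens. Randomisation alone then sets which agent is given. The sponsor should also state how this sentence fits with the regimens given elsewhere in the section; no dose or duration is proposed here.
2. **Replace the supervisor's manual coding.** Have the list generated and held where recruiting and treating clinicians cannot see it. A web randomisation system is one option; the plan allows that type of tool in general terms, but names no particular service.
3. **Vary the block sizes** and keep the block scheme in a document that recruiters do not see. One arm takes an oral drug and the other an injected one, and a double dummy is not clearly adopted, so past assignments may be visible on the ward.
4. **Release each assignment only after** eligibility is confirmed and the patient is irrevocably registered.
5. **State who recruits, who holds the list and who releases assignments.** Part of the section is in the past tense. If patients have already entered, record who held the code and when each assignment became known.

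The cost is protocol wording, a small set-up effort and a few minutes per patient. The documents do not show what service or staff the hospital already has, so any further cost is for the sponsor to check.
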